## 6.7.2 Adherence within the Simultaneous Treatment Group

1151 1152

## 6.8 Recurrence of Amblyopia

The proportion of participants who meet criteria for stable resolved and then have a recurrence of amblyopia will be tabulated within each treatment group and an exact 2-sided 95% confidence interval will be computed on the proportion within each treatment group.

1171 1172 1173

1174

1175

1176

Recurrent amblyopia is defined as a decrease in amblyopic eye VA of 0.2 logMAR or more and a 0.2 logMAR or more interocular difference of distance VA between the amblyopic eye and the non-amblyopic eye on a subsequent visit compared to the visit at which the definition of "stable resolved" was met. VA is calculated for each eye as the mean of the test and retest VA measurements made at the visit.

1177 1178 1179

1185

1186

1187

1188 1189

#### **6.9** Protocol Adherence and Retention

- 1180 A flow-chart will summarize visit completion by randomized treatment group.
- The proportion of participants within each randomized treatment group receiving non-
- randomized treatment at any time during the study will be calculated and will include the following:

1183 following

- The proportion of participants within the sequential patching treatment group who initiate patching prior to meeting stable residual amblyopia criteria (as defined in *section 4.3*).
- The proportion of participants within either group who receive a non-randomized treatment other than patching.
- The proportion of participants within the simultaneous treatment group who are non-compliant with patching, defined as never wearing a patch.

## **6.10** Baseline Descriptive Statistics

Baseline demographic and clinical characteristics will be tabulated by randomized treatment group.

#### **6.11 Subgroup Analyses**

An analysis to evaluate potential effect modification (interaction) between baseline amblyopiceye distance VA and randomized treatment will be conducted. It is possible that participants with worse baseline amblyopic eye VA may have different improvement by treatment assignment compared with participants with less severe amblyopia. The more severe amblyopes may have additional benefit from sequential treatment due to improved adherence with patching because of better VA after initial improvement with spectacles. On the other hand, the more severe amblyopes may benefit more from simultaneous treatment because patching is starting sooner. We will construct a 95% confidence interval for the baseline amblyopic eye VA by treatment group interaction term to test the hypothesis that there is a non-zero interaction between baseline amblyopic eye VA and treatment assignment. In addition, the treatment effect and 95% confidence interval for treatment effect will be calculated within subgroups defined by baseline amblyopic eye VA as moderate (VA 20/40 to 20/80, 68 to 53 letters) versus severe (20/100 to 20/200 (52 to 33 letters).

The following subgroup analyses, will be considered exploratory:

- Sex (male vs female)
- Race/ethnicity (white non-Hispanic vs non-white or Hispanic)
- Type of amblyopia (strabismic, anisometropic, or both)
- Binocularity as measured by the Randot Preschool, Randot Butterfly, and Worth 4-Shape tests

The approach for these analyses will be to estimate the treatment effect and 95% confidence interval within each subgroup (male versus female, white non-Hispanic versus non-white or Hispanic, type of amblyopia); using the same analytic methods as for the primary analysis. The interaction between treatment assignment and binocularity will also be explored.

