  - 5. For participants not already prescribed spectacles meeting eligibility criteria prior to enrollment, a single measurement of best-corrected VA in each eye, measured using the investigator's preferred VA testing method, must meet the criteria specified below. The refractive correction should correct for the full cycloplegic refractive error if the child is cyclopleged. If the child is not cyclopleged, the refractive correction should meet the refractive error prescribing criteria specified in Section 2.3 #4.
    - VA in the amblyopic eye approximately 20/40 to 20/200 (0.26 to 1.04 logMAR inclusive, 33 to 72 letters inclusive)
    - Age-normal VA in the fellow eye:
      - o 3 years: approximately 20/50 or better,  $\leq$  0.44 logMAR,  $\geq$  63 letters
      - 4 years: approximately 20/40 or better,  $\leq$  0.34 logMAR,  $\geq$  68 letters
      - 5-6 years: approximately 20/32 or better,  $\leq$  0.24 logMAR,  $\geq$  73 letters
      - o 7-12 years: approximately 20/25 or better,  $\leq 0.14 \log MAR$ ,  $\geq 78 \log MAR$
    - Interocular difference  $\ge 3 \log MAR$  lines (0.3 logMAR) or  $\ge 15$  letters
    - When participants return for the Spectacle Baseline / Randomization Visit with their new spectacles, they will need to meet the same criteria as above using the ATS-HOTV or E-ETDRS protocol after wearing the new spectacles for at least 10 minutes (based upon the mean of a test and retest of VA in those new spectacles).
  - 6. Investigator is willing to prescribe spectacle wear followed sequentially by patching or simultaneous spectacles and patching treatment per protocol.
  - 7. Parent and participant willing to forego option of contact lens wear for the duration of the study.
  - 8. Parent understands the protocol and is willing to accept randomization.
  - 9. Parent has phone (or access to phone) and is willing to be contacted by Jaeb Center staff or other study staff.
  - 10. Relocation outside of area of an active PEDIG site for this study within the next 56 weeks is not anticipated.

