## 2. Distance VA Testing:

- Monocular distance VA testing will be performed in refractive correction in each eye by a certified examiner using the electronic ATS-HOTV VA protocol for children <7 years and the E-ETDRS VA protocol for children ≥ 7 years on a study-certified acuity tester displaying single surrounded optotypes.
- The VA protocol used at enrollment will be used throughout the study regardless of age at follow-up.
- 2. Repeat Distance VA Testing: Monocular distance VA testing will be performed in current refractive spectacle correction in each eye by a certified examiner (as above).

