3.2 Randomization

528	For each age cohort, the Jaeb Center will construct a Master Randomization List using a			
529	permutated block design stratified by VA in the amblyopic eye (calculated as a mean of the test			
530	and retest) as moderate 20/40 to 20/80 (53 to 72 letters; 0.26 to 0.64 logMAR) versus severe			
531	20/100 to 20/200 (33 to 52.5 letters; 0.65 to 1.04 logMAR) which will specify the order of			
532	treatment group assignments.			
533				
534	All eligible participants enrolled in the study will be followed for up to 56 weeks. Participants			
535	eligible for randomization will be randomly assigned within each age cohort in a 1:1 allocation			
536	to one of the following treatment groups:			
537				
538	1. Sequential treatment : full-time spectacle correction first, with subsequent patching for 2			
539	hours per day/7 days per week only if needed (no improvement (stable/worsening) and			
540	residual)			
541	2. Simultaneous treatment: full-time spectacle correction and part-time patching for 2			
542	hours per day/7 days per week			
543				
544	Once a participant is assigned to a treatment group, the participant will be included in the			
545	analysis regardless of whether or not the assigned treatment is received. Thus, the investigator			
546	must not enroll and randomize a child unless convinced that the parent will accept either			
547	treatment.			

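### The severity subgroup ranges in section 6.11 do not carry over the stratum limits, so baselines of 68.5 to 72 and 52.5 letters belong to neither subgroup

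*Protocol*

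**What the plan says.** Three places in the protocol set limits on baseline amblyopic-eye acuity.

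- **Section 2.3 (eligibility):** "VA in the amblyopic eye approximately 20/40 to 20/200 (0.26 to 1.04 logMAR inclusive, 33 to 72 letters inclusive". Final eligibility uses the mean of a test and a retest.
- **Section 3.2 (Randomization):** a "permutated block design stratified by VA in the amblyopic eye (calculated as a mean of the test" and retest. The strata are "moderate 20/40 to 20/80 (53 to 72 letters; 0.26 to 0.64 logMAR) versus severe" "20/100 to 20/200 (33 to 52.5 letters; 0.65 to 1.04 logMAR".
- **Section 6.11 (Subgroup Analyses):** treatment effects with 95% confidence intervals are to be calculated within "moderate (VA 20/40 to 20/80, 68 to 53 letters) versus severe (20/100 to 20/200 (52 to 33 letters". No logMAR limits are given.

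Section 6.11 first describes an interaction between baseline amblyopic-eye acuity and treatment, and then adds the moderate and severe estimates. The subgroups labelled exploratory (sex, race/ethnicity, amblyopia type, binocularity) are listed separately afterwards. Under section 6.2, all analyses are run separately in each age cohort.

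**The concern.** Sections 3.2 and 6.11 use the same Snellen labels, 20/40 to 20/80 and 20/100 to 20/200, but print different letter limits under them. Section 3.2 covers every eligible value. Section 6.11 stops at 68 letters at the better end and goes from 53 straight to 52 at the division, although a mean of two whole-letter scores can be a half letter.

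An analyst who follows section 6.11 literally must leave some randomized children out of both severity estimates, including those with the mildest amblyopia. The alternative is to depart from the text, perhaps after seeing data. Severity is the one subgroup factor set apart from the exploratory list, and the protocol gives reasons why severe amblyopia might favour either strategy. The two subgroup estimates are what a reader would use to interpret any interaction.

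**Working it through.** **Inputs.** Eligible range 33 to 72 letters, 0.26 to 1.04 logMAR (section 2.3). Strata from section 3.2. Subgroup ranges from section 6.11. Baseline is the mean of test and retest (sections 2.3 and 3.2). Children under 7 years are tested with ATS-HOTV and older children with E-ETDRS (section 3.1.3).

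**Step 1: the protocol's own conversion.** The pairs 72 letters = 0.26 and 33 letters = 1.04 give a slope of (33 − 72)/(1.04 − 0.26) = −50, so

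letters = 85 − 50 × logMAR.

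This reproduces the other stratum limits: 85 − 50 × 0.64 = 53 and 85 − 50 × 0.65 = 52.5. It also reproduces the fellow-eye limits in section 2.3: 0.44 gives 63, 0.34 gives 68, 0.24 gives 73 and 0.14 gives 78.

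**Step 2: E-ETDRS values.** The mean of two whole-letter scores moves in half letters. From 33 to 72 there are (72 − 33)/0.5 + 1 = 79 possible values.

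| | Section 3.2 | Section 6.11 |
|---|---|---|
| Moderate | 53 to 72: 39 values | 53 to 68: 31 values |
| Severe | 33 to 52.5: 40 values | 33 to 52: 39 values |
| In neither | 79 − 79 = 0 | 79 − 70 = 9 |

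The nine values are 52.5 and 68.5, 69, 69.5, 70, 70.5, 71, 71.5 and 72 (0.65 logMAR, and 0.33 down to 0.26). No value that section 6.11 classifies is moderate in one section and severe in the other.

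**Step 3: HOTV values.** The worked examples in section 4.3.7 show means in steps of 0.05 logMAR. The eligible means are 0.30, 0.35, and so on to 1.00, which is 15 values.

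- A mean of 0.65, for example one test at 20/80 and one at 20/100, converts to 52.5 letters. It is severe in section 3.2. In section 6.11 it falls between the Snellen labels and between the letter ranges, so it is unassigned on either reading.
- A mean of 0.30 is 20/40 and converts to 70 letters. It lies inside the section 6.11 Snellen label and outside its letter range. It is unassigned only if the letter limits are applied to HOTV scores.
- The other 13 means are classified identically in both sections.

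**Step 4: internal consistency of section 6.11.** Because 20/40 corresponds to 70 letters, the moderate label and the letter range printed beside it disagree.

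**Step 5: after the change.** With the section 3.2 limits in section 6.11, unclassified values fall from 9 to 0 on the letter scale and from 2 to 0 among HOTV means.

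**The case against.** The case for leaving this alone is that the intent is plain. The Snellen labels match, so the authors evidently meant the same two categories. The protocol's change history says acuity equivalents were revised for the mean of two measurements in the eligibility and spectacle baseline chapters, and section 6.11 may simply have been missed. That explanation is plausible, but it leaves a rule that cannot be followed literally without dropping eligible children.

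Four stronger readings are tempting, and the protocol does not support them.

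- **Different severity cut-points.** A reader might infer that children move between moderate and severe. They do not: 53 letters and above is moderate in both sections.
- **A compromised interaction test.** That term is described on baseline amblyopic-eye acuity, with no reference to the letter ranges. The categories enter only through the additional within-subgroup estimates.
- **Lost balance or bias.** Both section 6.11 ranges lie inside the randomization strata, so comparisons within them remain randomized.
- **A sizeable share of the 272 younger children.** The protocol gives no baseline acuity distribution, and these children are tested with HOTV, where only a mean of 0.65 is clearly unassigned.

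The eligibility rule also thins the better end. An interocular difference of at least 0.3 logMAR or 15 letters means a child at 0.30 logMAR needs a fellow eye of 0.00 or better, and a child at 72 letters needs a fellow eye of at least 72 + 15 = 87 letters. This limits the number affected but does not remove the gap.

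**Conclusion.** Section 6.11 is wrong as written, and the error is minor. Nine of 79 eligible half-letter values belong to neither severity subgroup. This count is of possible scores and says nothing about the share of children, which the protocol does not allow anyone to compute.

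The letter gap bears directly on the older, E-ETDRS-tested cohort, for which section 6.13 sets no powered hypothesis test. In the younger cohort the clear gap is a mean of 0.65 logMAR, with 0.30 depending on how HOTV scores are read.

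The consequence is confined to the within-subgroup treatment effects and their confidence intervals. The primary analysis, sample size and interaction test lose nobody, provided the interaction is fitted on baseline acuity as section 6.11 describes.

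**What to change.** In section 6.11, replace the printed ranges with the section 3.2 categories and state that they apply to the mean of test and retest: moderate 0.26 to 0.64 logMAR (53 to 72 letters) and severe 0.65 to 1.04 logMAR (33 to 52.5 letters). Giving both scales removes any doubt about how HOTV scores are classified. Use the same limits wherever the statistical analysis plan repeats the subgroup definition.

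The cost is one line of text. No new data are needed, because baseline acuity on this mean already determines each child's stratum at randomization. The change is best made before any subgroup results are seen.

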#### 6.4 Primary Efficacy Outcome – Distance Visual Acuity in Amblyopic Eye

902 903

904

The primary efficacy outcome will be mean change in amblyopic eye logMAR distance VA between randomization and completion of randomized treatment or at 56 weeks, whichever is earlier.

905 906 907

The outcome VA for each participant is defined as either of the following:

908 909 910

911

1. Amblyopic eye VA (calculated as mean of test and retest) at the last visit that was the basis for a "stable resolved" or "stable residual" determination (in the sequential group, stable residual amblyopia criteria can be reached only *after* patching has been instituted); or

912 913 914

915

2. 56-week visit amblyopic-eye VA (calculated as mean of test and retest) in those completing a 56-week visit without ever meeting criteria for "stable resolved" or "stable residual" amblyopia (if retest missing at 56 weeks, the single test value will be used).

The outcome VA for participants who never meet criteria for "stable resolved" or "stable residual" amblyopia and do not complete the 56-week visit, or receive non-randomized treatment for amblyopia prior to meeting criteria for "stable resolved" or "stable residual" amblyopia, will be imputed using multiple imputation based on amblyopic eye VA scores while on randomized treatment (using the mean of test and retest if done).

The primary analysis will follow the intent-to-treat (ITT) principle whereby all participants randomized will be included in the analysis according to the treatment group assigned at randomization. An analysis of covariance (ANCOVA) will be performed to compute the difference in mean change in amblyopic-eye distance VA (in logMAR lines) between the sequential and simultaneous treatment groups, adjusted for baseline amblyopic eye distance VA, and a 2-sided 95% confidence interval will be constructed on the treatment group difference. Equivalence of treatment groups will be declared if the upper and lower 95% CI limits are smaller (in absolute value) than the equivalence margin of 0.75 logMAR lines. Superiority of one treatment over the other will be declared if the upper and lower ends of the 95% CI exclude 0 difference.

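### Section 6.11 plans only separate within-subgroup intervals for sex, race/ethnicity and amblyopia type, so it gives no estimate of whether the treatment effect differs between their levels

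*Protocol*

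**What the plan says.** Protocol section 6.11 handles its factors in two ways.

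- **Baseline amblyopic-eye acuity** gets a formal interaction: "We will construct a 95% confidence interval for the baseline amblyopic eye VA by treatment group interaction term". Effects in the moderate and severe groups are reported in addition.
- **Sex, race/ethnicity, amblyopia type and binocularity** come under the statement "The following subgroup analyses, will be considered exploratory". For the first three the approach is fixed as follows: "The approach for these analyses will be to estimate the treatment effect and 95% confidence interval within each subgroup", "using the same analytic methods as for the primary analysis". Binocularity is treated differently: "The interaction between treatment assignment and binocularity will also be explored".

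No interaction term is named for sex, race/ethnicity or amblyopia type.

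Section 6.4 sets two decision rules for the overall comparison. On equivalence, with a margin of 0.75 logMAR lines: "Equivalence of treatment groups will be declared if the upper and lower 95% CI limits are smaller (in absolute value) than the equivalence margin". On superiority: "Superiority of one treatment over the other will be declared if the upper and lower ends of the 95% CI exclude 0 difference". Section 6.11 does not say whether these rules stop at the whole cohort. Section 6.2 has every analysis run separately in the younger and older cohorts.

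**The concern.** A subgroup analysis asks whether the treatment difference in one level departs from that in another. Two separate intervals do not answer this. One can exclude 0 and the other include it when the two estimates hardly differ, and two overlapping intervals can hide a real difference. The section uses the right tool for two factors and gives no reason for leaving it out for the other three.

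The design adds to the risk of misreading. In an equivalence trial readers have two reference points, 0 and 0.75 lines, and will hold each subgroup interval against both. The smaller the subgroup, the more readily its interval crosses 0.75 through lack of precision alone. At stake are secondary statements that treatment works differently by sex, race/ethnicity or cause of amblyopia. The primary result is not at stake.

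**Working it through.** **Inputs from the protocol.** SD 1.7 lines, 272 children (136 per group), true difference 0, margin 0.75 lines, one-sided type I error 2.5% (section 6.12.4). Sex has 2 levels, race/ethnicity 2 and amblyopia type 3 (section 6.11), so there are 7 intervals per cohort.

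**Assumed, because the protocol gives no subgroup shares.** Sex 50/50; race/ethnicity 50/50 or 60/40; type in thirds, 25/50/25 or 15/60/25. The factors are taken as independent of one another.

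**The plan's own figures.**
- Per arm, n = 2 × (1.7 × (1.960 + 1.645) / 0.75)² = 133.5, so 134 per arm or 268 in total, against 272 stated. The exact t-based power at 136 per arm is 90.4%. The stated size is sound.
- In Table 4, the half-width at N = 75 and SD 1.7 is 1.96 × 1.7 × √(4/75) = 0.77 (0.78 with the t quantile), against 0.78 stated.

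**Chance that some subgroup interval excludes 0 when there is no effect.** Each interval does so 5% of the time. Seven independent intervals would give 1 − 0.95⁷ = 30.2%. The factors overlap, since every child appears once under each, so the true figure is lower. Simulating 8,000 trials per scenario gave 25.2%, 25.2% and 25.0% for the three sets of shares. Among trials that showed overall equivalence it was about 19%. The result hardly depends on the shares.

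**Subgroup size at which the half-width reaches 0.75.** With equal arms, half-width = 1.96 × SD × 2/√N, so N = (1.96 × SD × 2 / 0.75)².
- SD 1.7: (6.664 / 0.75)² = 79.
- Over the SDs in Table 3: SD 1.6 gives 70, SD 1.9 gives 99.

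At SD 1.7, with t quantiles, the half-widths are:

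| Subgroup N | Share of 272 | Half-width (lines) |
|---|---|---|
| 136 | 50% | 0.58 |
| 109 | 40% | 0.65 |
| 91 | 33% | 0.71 |
| 68 | 25% | 0.82 |

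These take no credit for adjustment for baseline acuity, which may narrow them.

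**With one interaction test per factor.** Three tests at 5% give 1 − 0.95³ = 14.3%. The same simulations, with a joint two-degree-of-freedom test for type, gave 14.8%, 14.2% and 14.6%.

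**Power of an interaction test at a 50/50 split.**
- SE in one level: 1.7 × √(2/68) = 0.292.
- SE of the difference between levels: 0.292 × √2 = 0.412.
- Power for a 0.75-line interaction: Φ(0.75/0.412 − 1.96) = Φ(−0.14) ≈ 44%.

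**The case against.** The other side has a good case on several points.

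- **The decision rules are not imported.** A reader might infer that each subgroup will be declared equivalent, not equivalent or superior under section 6.4. The text does not support this. It carries over analytic methods, which most naturally means the ANCOVA, the baseline adjustment and the imputation. The rules in 6.4 are worded for the treatment groups as a whole, and no rule there labels a failure to show equivalence as non-equivalence. If the rule were applied, a half-sample of 136 would pass only 45% of the time under true equality, and the two sexes would disagree in about 2 × 0.45 × 0.55 = 49% of trials. That figure depends on a step the protocol never states.
- **The analyses are labelled exploratory.** This limits the weight of any result, and it stands. It does not make separate intervals answer the interaction question.
- **Little information is lost.** The levels of a factor do not overlap, so a reader can approximate the contrast from the published estimates and intervals. This is largely true, but it leaves the relevant estimate to be worked out by the reader, and for the three-level factor it takes more than one comparison.
- **The statistical analysis plan may add interactions.** It may. Section 6.11 does not rule them out, but for these three factors it states what the approach will be, and that approach is the weaker one.
- **Interaction tests have low power.** Correct, and it is a real limit on the remedy.

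**Conclusion.** The point holds as a minor one. For sex, race/ethnicity and amblyopia type the protocol fixes a method that does not estimate the difference in effect between levels, while the same section uses interactions for baseline acuity and binocularity.

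Under no true effect, at least one of seven intervals excludes 0 in about 25% of trials per cohort, against about 14% for any false signal over three interaction tests. These figures rest on 5% error per interval or test and on assumed shares that hardly matter. The threshold of about 79 children rests on SD 1.7 without baseline adjustment.

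Two stronger conclusions do not follow. A false superiority signal is possible but not likely, at about one trial in four. Nor can it be said that a subgroup below 79 could never fall inside the margin: the observed SD varies and ANCOVA may reduce it. Even unadjusted, the equivalence rule would be met about 1% of the time at N = 68. The primary conclusion is unaffected.

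**What to change.** In section 6.11:

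1. For each of sex, race/ethnicity and amblyopia type, fit the primary ANCOVA with the factor and a treatment-by-factor term, and report the interaction estimate with its 95% CI. For the three-level factor, give the contrasts and one joint test.
2. Keep the within-subgroup estimates and intervals, described as descriptive.
3. State that the equivalence and superiority rules of section 6.4 are not applied within subgroups.
4. State that an interaction interval including 0 is not evidence that the effect is the same across levels.

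The cost is three extra model fits per cohort and two sentences, with no new data and no change in sample size. The small downside is the low power (about 44% for a 0.75-line interaction at an even split), which the fourth sentence addresses.
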